After instrumentation (described below) and an initial period of 20 min of rest, participants will undergo baseline testing which consists of arterial stiffness (pulse-wave velocity and ultrasound) and carotid distensibility. Next, participants will undergo 3 separate conditions separated by 20 minutes of quiet rest: **1)** 3 min with their hand in an ice bath (cold pressor test); **2)** Flow mediated dilation (~15 minutes) and **3)** an end expiratory breath hold (~15s). Following the cold pressor test a heating pad will be used to warm the hand to baseline temperature.

**Postpartum Visit)** Participants will arrive after refraining from exercise, caffeine, alcohol or food for 12 h (overnight fast) and blood samples will be collected. Following the blood draw, anthropometrics will be recorded and a standardized breakfast will be provided. Participants will then undergo an assessment of blood vessel health. After instrumentation (described below, but without microneurography), participants will undergo testing which consists of arterial stiffness (pulse-wave velocity and ultrasound) and carotid distensibility. Following this, participants will undergo an assessment of flow mediated dilation (described above).

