### **3.4 Statistical Plan**

#### *Sample Size Determination*

Our primary hypothesis is that exercise training will reduce resting SNA (burst/min) in pregnant women. Data from other clinical populations with high resting SNA indicates a ~23% decrease in resting SNA with exercise training (4). Previous data collected in our lab demonstrate a resting burst frequency of  $40 \pm 11$  burst/min. Based on previous findings we expect exercise training to reduce resting SNA to  $\sim 31 \pm 11$  bursts/min (-23%). Using these data we estimate 22 pregnant women are required to observe a significant reduction in SNA following exercise training (80% power,  $\alpha = 0.05$ ; G\*Power v3.16 (10)). We expect an 80% success rate for obtaining an appropriate SNA signal and an 80% retention rate, requiring 43 women to be recruited into the

training arm of the study. To allow for additional variability and or decreased retention we will recruit 50 pregnant women to take part in exercise training and 50 pregnant women to take part as controls.

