#### *Statistical Methods*

To assess our primary outcome (the difference in basal SNA between groups) a 2 way mixed model (group x time) ANOVA will be used. To assess the influence of exercise on our secondary outcomes (i.e. vascular function and blood markers) a similar 2 way mixed model design will be used. Tukey's post hoc analysis will be used to compare means when main effects are found to be significant.

The strength of the association between changes in SNA, vascular measures and blood markers within and across groups will be determined using the Pearson product-moment correlation coefficient. Statistical analyses will be performed using SPSS Version 16.0 (SPSS, Chicago, IL). Statistical significance will be assumed at  $P < 0.05$ .

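### Tukey after significant main effects is the only follow-up rule: for SNA it either repeats the F test or, if run over the four group-by-visit means, has no single suitable error term, and no planned exercise-control contrast is named

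*Combined protocol and SAP*

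**What the plan says.** All statements on the analysis are in section 3.4.

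- Primary outcome: "To assess our primary outcome (the difference in basal SNA between groups) a 2 way mixed model (group x time) ANOVA will be used".
- Secondary outcomes: "a similar 2 way mixed model design will be used".
- Follow-up to both: "Tukey's post hoc analysis will be used to compare means when main effects are found to be significant".

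The section does not say which means form the Tukey family, which error term is used or which comparison is the key one. It gives no contrast, standard error or confidence interval for the between-group difference in SNA.

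The General Design section fixes the number of SNA visits. Instrumentation at the postpartum visit is "described below, but without microneurography", so SNA is recorded at 16-20 and 34-36 weeks only. Arterial stiffness, carotid distensibility and flow mediated dilation are measured postpartum as well.

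**The concern.** Tukey's procedure controls error over all pairs of means, and in its classical form it uses one error term for every pair. On a two-level factor there is only one pair, so it adds nothing to the F test. For SNA it can do extra work only across the four group-by-visit means. Those give six pairs: some compare different women (exercise against control) and some the same women (34-36 weeks against baseline). The two kinds have different standard errors.

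The sentence therefore leaves the analyst a choice, possibly after the data are seen, between a redundant procedure and an ill-fitting one. At stake are the pairwise P values and intervals that readers would quote, in particular for exercise against control at 34-36 weeks.

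**Working it through.** **Inputs.** From Sample Size Determination: resting SNA 40, SD 11 bursts/min; expected 31, SD 11 ("a ~23% decrease in resting SNA with exercise training"), a difference of 9; alpha 0.05, taken as two-sided because the plan does not say. The pre-post correlation r is not in the documents; 0.3, 0.5 and 0.7 are assumed. Equal variances are assumed. The between-woman term here means the ordinary variance among women at one visit (SD 11).

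**The plan's own figure.** The plan states: "we estimate 22 pregnant women are required to observe a significant reduction in SNA following exercise training". By the normal approximation, n per arm = 2 × (1.960 + 0.842)² × 11² / 9² = 23.4, so 24. With 9.2 (23% of 40) it is 22.4, so 23. Both are close to 22, read as per arm because the plan inflates it to 43 for the training arm.

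**Evaluable women per arm.** 22/0.8² = 34.4, but 22/0.8³ = 42.97, so the 43 implies three 80% factors although two are stated. Applied to 50 per arm, three factors leave 50 × 0.8³ = 25.6 and two leave 50 × 0.8² = 32. Both are shown, with 22 and the full 50.

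**Tukey on a two-level effect.** With 48 df, q(0.95; 2)/√2 = 2.011 and t(0.975) = 2.011. They are the same test, with no loss.

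**Tukey over four means, between-woman term.** SE = 11 × √(2/n); noncentrality = 9/SE; critical values t(0.975, 2n−2) and q(0.95; 4, 2n−2)/√2. At n = 25: SE = 3.111, noncentrality 2.89, critical values 2.011 and 3.764/√2 = 2.661.

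| Evaluable per arm | Single contrast | Tukey, four means | Loss (points) |
|---|---|---|---|
| 22 | 75.5% | 52.1% | 23.4 |
| 25 | 80.9% | 59.4% | 21.5 |
| 32 | 89.6% | 73.4% | 16.2 |
| 50 | 98.2% | 92.8% | 5.4 |

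With 4n−4 df the losses are less than one point smaller. Under this term the between-arm standard error is right, but within-arm changes get one that is too large by 1/√(1−r): 20%, 41% and 83% at the three correlations. In simulation at 22 per arm (20,000 trials per setting), the null rejection rate for a within-arm pair was 0.3% or less, against about 1% intended.

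**Tukey over four means, within-woman residual.** The between-arm standard error is multiplied by √(1−r), so the effective critical value is 2.661 × √(1−r). Figures are for 25 per arm, 48 df.

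| r | √(1−r) | Effective critical t | Per-pair error (intended 1.1%) | Power (single contrast 81%) |
|---|---|---|---|---|
| 0.3 | 0.837 | 2.227 | 3.1% | 75% |
| 0.5 | 0.707 | 1.882 | 6.6% | 84% |
| 0.7 | 0.548 | 1.458 | 15.1% | 92% |

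Simulation at 22 per arm gave per-pair rates of 2.8%, 6.6% and 14.8%, and error over all six pairs of 10%, 17% and 30% instead of 5%.

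**The recommended contrast.** Adjusting for baseline multiplies the standard error by √(1−r²). At 25 per arm, power rises from 81% unadjusted to 84% at r = 0.3 and 98% at r = 0.7.

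**The case against.** The strongest reply is that the plan does not commit to the faulty use. It ties Tukey to main effects, never mentions the four cells and names no error term. Read literally, the sentence costs nothing for SNA. That stands: a reader might infer that Tukey with a single error term is prescribed for the repeated-measures means, and the text does not support this. What remains is that the literal reading leaves SNA with no useful follow-up, and the only use that would add anything is unspecified and fits badly.

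Three other stronger readings also fail.

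- *The trial's primary test loses about 20 points of power.* The primary outcome is assessed by the ANOVA, and its interaction test pays no Tukey charge. The loss belongs to a follow-up pair taken alone, leaving aside the requirement that a main effect be significant first.
- *The power loss and the too-narrow between-arm interval occur together.* They are alternatives. The 21 to 23 points need the between-woman term, under which the between-arm standard error is correct. With the residual at 25 per arm, Tukey's power is 6 points below the single contrast at r = 0.3, and 3 and 11 points above it at 0.5 and 0.7.
- *Outcomes with a postpartum visit share the fault.* Tukey on a three-level time main effect compares the same women throughout and, given sphericity, has one proper error term. It is not faulted here.

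Contrast-specific standard errors from the model would largely cure the interval problem, but the plan does not specify them.

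**Conclusion.** The concern holds in a conditional form. The sole follow-up rule is redundant for SNA on main effects, and unsuitable if carried to the four group-by-visit means, where one kind of pair is wrong under either single error term. Which harm would arise depends on a choice the plan leaves open: overly wide within-arm intervals and lost follow-up power, or between-arm intervals that are too narrow.

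The power loss depends on the number evaluable, and 22 to 25 per arm is the unfavourable end of the range. The error-rate figures rest on the assumed correlations. Neither describes the ANOVA. The point is worth acting on because the plan defines its primary outcome as a difference between groups, yet names no estimate of that difference.

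**What to change.** For group comparisons, replace the Tukey sentence with one planned contrast: exercise minus control in basal SNA at 34-36 weeks, adjusted for the baseline value already collected, estimated from the mixed model with its own standard error and 95% CI, and tested once at 0.05. Report within-arm changes descriptively, with contrast-specific standard errors. For outcomes with a postpartum visit, use visit-specific exercise-control contrasts from the model, with Holm's adjustment if more than one is tested.

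The cost is a change of wording and the loss of all-pairs P values. No extra data or participants are needed.

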#### *Tertiary Outcome variables*

**A) Insulin and glucose measurement.** Insulin has been shown to increase SNA in healthy and diabetic individuals (14). Vascular (both peripheral and cerebral) function is altered by these hormones. As insulin resistance increases during pregnancy, fasted measures of glucose and insulin (Day1) will be analyzed to

determine their relationship to the primary outcome measures. Insulin sensitivity will be determined using the HOMA equation (18).

**B) Arterial Stiffness and Endothelial-dependant Dilation.** Arterial stiffness and endothelial function will be assessed to determine the influence of exercise on other measures of vascular function.

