### 3.2 Subject Selection and Withdrawal

One hundred pregnant women (>18yrs, with singleton pregnancies) will be recruited between 16-20 weeks gestation through physician and midwife referrals, newspaper advertisements and recruitment posters. Women diagnosed with multiple pregnancies will be excluded. Eligible women will be randomized to take part in an exercise intervention (n=50) or no intervention (n=50). The intervention will consist of aerobic exercise equivalent to 50-70% of heart rate reserve, 3-4 times per week until the end of the study (34-36 weeks). For initial baseline testing (16-20 weeks) and at the end of the intervention (34-36 weeks), participants will visit the laboratory twice. Following initial baseline testing, women will be randomly assigned to an exercise intervention or no intervention. Women will receive an opaque sequentially numbered envelop with their allocation. Allocation will be determined using a randomly generated allocation sequence by an individual not associated with the research study who will place and seal the allocation in the envelope.

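### The across-group Pearson correlations of change scores carry no adjustment for randomised arm, so they can mix the training effect into the association; a group-adjusted coefficient would avoid this at almost no cost

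*Combined protocol and SAP*

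**What the plan says.** Under Statistical Methods (section 3.4), the primary and secondary outcomes are compared by a group-by-time mixed ANOVA. A separate sentence covers associations: "The strength of the association between changes in SNA, vascular measures and blood markers within and across groups will be determined using the Pearson" product-moment coefficient. No group term, partial correlation or regression is named for the across-group version. The plan does not say whether the within-group or the across-group coefficient carries the inference. The general threshold applies to both: "Statistical significance will be assumed at" P < 0.05.

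Section 2.2 hypothesises that exercise will blunt the pregnancy-related rise in SNA and will also reduce vascular reactivity to sympathetic stressors. Training is therefore expected to move at least two of the kinds of variable being correlated, and in the same direction.

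**The concern.** A Pearson coefficient computed on two randomised arms together has two sources of covariance. One is how the two changes vary together among women in the same arm. The other is the product of the two differences in arm means. The second source is present whenever training moves both variables, even if a woman's SNA change says nothing about her vascular change.

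A reader of a significant across-group r would naturally conclude that women whose SNA fell more also had larger vascular changes. That reading is unsafe in the situation the investigators hope for, where exercise works on both. The arm difference can also oppose the within-arm association and conceal it. What is at stake is a mechanistic interpretation; the test of whether exercise works does not depend on it.

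**Working it through.** **Inputs from the documents**
- Allocation is 1:1, 50 per arm (section 3.2).
- SNA effect (Sample Size Determination): "Previous data collected in our lab demonstrate a resting burst frequency of" 40 ± 11 bursts/min, and "we expect exercise training to reduce resting SNA to" about 31 ± 11. The difference is 9.
- Losses (same section): 80% signal success and 80% retention.
- Test level 0.05, taken as two-sided because no sidedness is stated.

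**Inputs not in the documents (assumed)**
- Correlation of SNA between visits, ρ. It sets the SD of change, 11 × √(2(1 − ρ)). The central value is ρ = 0.5, which gives an SD of change of 11.
- Training shift in the second variable, d2, in SDs of its change: 0 to 0.82.
- The fall of 9 is taken as the between-arm difference in change. Losses are equal in both arms, and the changes are bivariate normal.

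**The plan's own figures.** The normal approximation for two means gives 2 × (1.960 + 0.842)² × 11²/9² = 23.5, so 24 per arm. With an exact 23% fall (9.2) it gives 22.4, so 23. The plan's 22 is close. Its 43 is reproduced by 22/(0.8 × 0.8 × 0.8) = 42.97, which counts signal success at two visits plus retention. The same factor gives 100 × 0.512 = 51 women with paired SNA, taken here as 25 per arm. The plan states no figure for the correlation analysis; its sample-size section supplies only the effect size and the evaluable number.

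**Formula.** With equal arms, within-arm correlation r_w and standardised shifts d1 and d2:

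pooled r = (r_w + d1·d2/4) / √[(1 + d1²/4)(1 + d2²/4)]

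**Central case.** r_w = 0 and d1 = 9/11 = 0.82. For d2 = 0.82: d1·d2/4 = 0.167, and pooled r = 0.167/1.167 = 0.14. Rejection rates are simulated at 25 per arm.

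| d2 (SD) | Pooled r | Pooled test rejects | Arm-adjusted test rejects |
|---|---|---|---|
| 0 | 0.00 | 5% | 5% |
| 0.3 | 0.06 | 7% | 5% |
| 0.5 | 0.09 | 10% | 5% |
| 0.82 | 0.14 | 17% | 5% |

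**Sensitivity to ρ**, with d2 = d1, r_w = 0 and 25 per arm:
- ρ = 0 (SD of change 15.56, d1 = 0.58): pooled r 0.08, rejection 8%.
- ρ = 0.3 (13.02, 0.69): 0.11 and 12%.
- ρ = 0.7 (8.52, 1.06): 0.22 and 34%.

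With d2 held at 0.5, the rate over these same ρ values runs from 7.5% to about 13%.

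**Masking.** If r_w = −0.30 and both shifts are 0.82 SD in the same direction, pooled r = (−0.30 + 0.167)/1.167 = −0.11. About three-fifths of the within-arm association disappears.

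**Cost of adjusting.** With r_w = 0.30 and no arm shift, power at N = 50 is about 57% for the pooled test (48 degrees of freedom) and 56% for the adjusted test (47).

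**The case against.** The strongest reply is that the same sentence already plans within-group correlations. These are free of the bias, and set beside a pooled r they could expose it. The plan also never says that inference rests on the pooled value, and 'across groups' is undefined. A pooled population r of 0.14 is, moreover, a genuine property of the pooled sample; the error lies only in reading it as an association between women within arms. All of this is fair and limits the point. It does not remove it. The within-group coefficients do not correct the across-group test, which falls under the same P < 0.05. They are also weak: at 25 per arm a true r of 0.30 is significant in a given arm only about 31% of the time. A significant pooled result with two non-significant arms could be put down to low power.

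The size also rests on assumptions. The SD of 11 describes resting level and equals the SD of change only if ρ = 0.5. No vascular measure or blood marker has an effect size in the documents. That objection stands, and it is why the result is given as a range.

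Three stronger readings are tempting and are not supported.
- A reader might infer that these correlations are the plan's only link between sympathetic and vascular change. They are not. Secondary outcome A follows femoral conductance over each SNA burst and the next 15 beats, and basal transduction and the cold pressor changes are compared between groups.
- A reader might infer that a spurious link is the expected result. Even with both shifts at 0.82 SD, about 83% of pooled tests at N = 50 are non-significant.
- A reader might extend the point to the insulin and glucose analysis, which is meant to "determine their relationship to the primary outcome measures". That text names neither Pearson nor pooling, and it refers to fasted measures, not to changes.

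**Conclusion.** The point holds as a minor one. On the natural reading, the across-group Pearson r is not a clean measure of association between women when training moves both variables, and its 5% level is then not kept for that question. In the central case the rate is about 7% to 17% for second-variable shifts of 0.3 to 0.82 SD, and 5% if only one variable responds. It rises further only if SNA is highly repeatable between visits and the second variable responds just as strongly. All of this assumes that 'across groups' means simple pooling. The hypothesised direction of both effects comes from section 2.2. It covers SNA and vascular reactivity only; no directional effect on the blood markers is hypothesised there.

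The primary group-by-time ANOVA, the secondary group comparisons and the vascular transduction outcome are unaffected.

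**What to change.** Replace the across-group Pearson coefficient with a group-adjusted one: either a partial correlation controlling for randomised group, or a regression of one change on the other with group as a covariate. Report it with its 95% CI and state that it carries the inference. Keep the separate within-group correlations as descriptive, and do not present an unadjusted pooled r as evidence of association. If adjustment was already intended, the same sentence makes that clear.

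The cost is one sentence of text and one degree of freedom, about one percentage point of power in the example above. No new data are needed.

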### **4 Data Handling and Record Keeping**

#### **4.1 Confidentiality**

After consenting to participate in the study, the participant will be given an identifying code which will be used for study identification from that point forward. Both name and date of birth will be retained on consent forms. Phone number, mailing address and email will be kept on subject information sheets. In addition, a master list linking participant identifiers with de-identified data will be retained in a locked cabinet within a locked room. Confidentiality agreements between the principal investigator and any other study personnel will be signed. All personnel will be made aware of the procedures for maintaining confidentiality and will be expected to not discuss the participants or results with any person not directly involved in the study.

#### **4.2 Records Retention**

No specific uses are planned for data beyond 5 years. All information related to personal identifiers will be destroyed at this time. However, non-identifiable data (including date of birth) will be kept indefinitely in the case that it may be informative in the future.

#### **4.3 Regulatory Binder**

A regulatory binder documenting all aspects (e.g. informed consent, questionnaires, adverse event forms, etc) will be maintained by the study investigators. This binder will be kept in a locked cabinet in a locked office to maintain confidentiality (see above).

